Strong Fathers, Stronger Families Healthy Marriage and Responsible Fatherhood Program Evaluation

Statistical Analysis Plan

Clinicaltrials.gov ID: NCT06907719

8/2/2023

1. Data Analysis

Briefly describe the planned approach for data analysis. If an impact analysis is proposed, name the key dependent and independent variables, and describe any methods to minimize Type I error (i.e., finding positive impacts by chance) such as limiting the number of impacts to be analyzed and/or multiple comparison correction. Describe proposed approach(es) for addressing missing data.

Identify study sample

The study sample includes participants who: 1) gave recorded informed consent to be part of the study, and 2) took both an entrance and exit survey. The CONSORT diagram in Appendix B shows exclusion criteria and the anticipated size of the overall study sample. The analytic sample for particular outcome measures will vary based on missing data.

Defining analysis measures

For each outcome construct, we have identified the relevant measures from nFORM that are theoretically aligned with that construct. We will generate a correlation matrix between items in a given construct to ensure that theoretically related items are also empirically related in our data set. Items that are not strongly correlated with other items in a construct will be removed as necessary. Factor analysis will be used to ensure that all construct items hang together (using an alpha of 0.7 or higher as the threshold).

Once we are confident that all of the items align with a given construct, we will create a composite measure by taking an average of the scores on each non-missing item in the construct. The measure definition matrix below provides information on each proposed outcome. For composite measures, a change score will be calculated between a participant's pre-program composite score and post-program composite score. For standalone survey items, a change score will be calculated between a participant's pre-survey and post-survey responses.

For the sake of consistency and simplicity, parenting and co-parenting analyses will use a participant's youngest child as the focal child.

	Sample		Data	Variable	
Measure		Variable Type	source(s)	Name	Definition
Co-	Has at least one child	Continuous	nFORM	Copar_Beh	Average of five
parenting	age 24 or younger	(range from 1 to 5	entrance,		survey items that
relationship			nFORM		relate to positive
behaviors			exit		interactions with

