		and 5 is strongly			the mother of
		agree)			participant's
					youngest child

	saw child within past month	(range from 1 to 5 where 1 is never			Average of 10 to 11 survey items (depending on child age) that relate to frequency of positive interactions with participant's youngest child
•	Has at least one child age 24 or younger, saw child within past month	(range from 1 to 24)	nFORM entrance, nFORM exit		Reported number of hours per day (excluding sleeping) that parent usually spent with their youngest child
Frequency of contact		(range from 1 to 4 where 1 is every	entrance, nFORM exit		Reported frequency of reaching out to youngest child in the past month
Economic stability – checking account	•	(0/1)	nFORM entrance, nFORM exit	_	Binary measure of having opened a checking account by the end of the program
Economic stability – savings account	_	(0/1)	nFORM entrance, nFORM exit	0 _	Binary measure of having opened a savings account by the end of the program
Economic stability – difficulty paying bills		(range from 1 to 4 where 1 is never		_	Reported frequency of difficulty paying bills

Handling missing data

Outcomes

When creating the composite measures for co-parenting and parenting relationships, we will create a composite score by taking the average of multiple individual items. For these measures, our current plan is to use 20% as a threshold for allowable missing items, based on guidance from evaluation technical assistance resources. This plan is contingent on the final distribution of missing data in our data set. With a 20% threshold, if a respondent is missing more than 1 item used for creating the coparenting construct or more than 2 items for creating the parenting construct, the respondent will be assigned a missing value for that construct. We will not be imputing truly missing values for outcomes. To create a construct score, the average will divide by the number of non-missing values in the construct.

Participants who have not seen their child within the past month will have their parenting behavior responses set to "Never" (1) and will be included in the analytic sample for that outcome.

For outcomes that use single survey items, participants who do not respond to the item on either the pre- or post-survey will be excluded from the analytic sample for that outcome.

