Missing data for the implementation outcomes could happen as a result of programmatic data entry issues. For the sake of this evaluation, we assume that any primary or support services received by a participant are being accurately logged into nFORM, so a lack of documented attendance, service contacts, referrals, etc. is indicative of lack of services (i.e., a participant not receiving the program components as intended).

...

Assessing non-response bias

We will conduct response rate analysis for each primary outcome of interest to assess non-response bias and adjust for threats to internal validity. Using data from the Applicant Characteristics Survey, we will look at demographics (race, ethnicity, age, education level) and primary reason for joining the program among participants who fall into each of the following categories: 1) non-respondents who answered no surveys after the ACS, 2) respondents who completed the pre-survey only, 3) respondents who completed the post-survey only, and 4) respondents who completed both the pre-and post-survey (complete case).

Analytic approach

The main goal of this descriptive study is to assess pre-post change scores in the outcomes listed above among program participants before and after primary workshops. We will use paired sample t-tests to assess the magnitude and significance of changes among program participants in the analytic sample for each outcome. For binary economic stability outcomes, we will descriptively report the percent of participants who opened a checking or savings account during the course of the

program. We will adjust our p-values for multiple hypothesis testing and report the adjusted p-values in the appendix of the final report.

For the implementation analysis, program fidelity will be descriptively reported by the percentage of enrolled participants who receive: 1) any primary workshops, 2) employment supports, 3) substantive service contacts, 4) referrals. The program aims to provide all participants each of these four program components, so the percentage of participants who receive each of these will be compared to the 100% benchmark. Number of substantive service contacts per participant will also be compared to the benchmark of 8 SSCs set by OFA for FIRE grantees.

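### The non-response comparison is promised per outcome but groups fathers only by surveys taken, so eligible fathers without a usable change score count as complete cases

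*SAP*

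**What the plan says.** All places are in SAP section 1.

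- **Identify study sample.** The overall sample is fathers who consented and "took both an entrance and exit survey". The SAP adds: "The analytic sample for particular outcome measures will vary based on missing data".
- **Handling missing data, Outcomes.** A composite is set to missing if more than 1 co-parenting item or more than 2 parenting items are blank. For single-item outcomes, "participants who do not respond to the item on either the pre- or post-survey will be excluded from the analytic sample for that outcome". Outcomes are not imputed. Fathers who have not seen the child in the past month are given the lowest score on the parenting behaviour items and kept.
- **Assessing non-response bias.** The promise here reads: "We will conduct response rate analysis for each primary outcome of interest to assess non-response bias and adjust for threats to internal validity". The groups compared on Applicant Characteristics Survey (ACS) data are "1) non-respondents who answered no surveys after the ACS", then "2) respondents who completed the pre-survey only, 3) respondents who completed the post-survey only", and finally "4) respondents who completed both the pre-and post-survey (complete case").
- **Analytic approach.** The paired t-tests are run on each outcome's own analytic sample. The two account outcomes are reported as percentages.

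Some outcomes also have a defined population. The SAP matrix requires a child aged 24 or younger (visible for the co-parenting and hours rows) and recent contact with the child for the hours item. Protocol section 9.1 limits each account outcome to fathers without that account at entry.

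**The concern.** Fathers leave an analysis at two points: by not taking a survey, and by taking both surveys but leaving the outcome unanswered. The four groups capture only the first. Because they do not refer to any outcome, group membership, and so the comparison table, is the same for every outcome.

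The group labelled complete case is therefore not the group tested. If fathers who skip questions about the child's mother, contact with the child or paying bills differ from those who answer, the planned comparison would not isolate them, and it could look reassuring for an outcome that lost many fathers at item level. Such selective skipping is plausible, but the documents give no evidence on it. It matters because R1 to R3 are confirmatory (protocol section 1.2) and the design is pre-post without a counterfactual (protocol section 5), so interpretation depends on who is in each analysed sample.

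**Working it through.** **1. The plan's own cut-offs reproduce.** Allowed missing items = 20% of the items, rounded down: 0.20 × 5 = 1; 0.20 × 10 = 2; 0.20 × 11 = 2.2, so 2. These match the SAP.

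**2. Groups against exclusions.**

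| Reason a father is not analysed | Own group in the comparison? |
|---|---|
| No survey after the ACS | Yes, group 1 |
| Entrance survey only | Yes, group 2 |
| Exit survey only | Yes, group 3 |
| Both surveys, single item blank at either | No, sits in group 4 |
| Both surveys, too many composite items blank | No, sits in group 4 |
| Outside the outcome's population | No, sits in group 4 if both surveys taken, but this is ineligibility |

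**3. How many both-survey fathers could be dropped.** No item-missing rate is given, so this is illustration only. Assume each item is blank with probability m, independently and equally at both surveys. With P the probability of exceeding the cut-off at one survey, the dropped share is 1 − (1 − P)². P is the binomial probability of 2 or more blanks of 5 (co-parenting), or 3 or more of 10 or 11 (parenting); for a single item P = m.

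| m | Co-parenting, 5 items | Parenting, 10 items | Parenting, 11 items | Single item |
|---|---|---|---|---|
| 2% | 0.77% | 0.17% | 0.23% | 3.96% |
| 5% | 4.47% | 2.29% | 3.02% | 9.75% |
| 10% | 15.63% | 13.55% | 17.11% | 19.00% |
| 15% | 30.24% | 32.73% | 39.35% | 27.75% |

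If whole blocks are skipped instead, at 5%, 10% or 20% per survey, the dropped share is 9.75%, 19.00% or 36.00%.

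**4. Share of all loss that lies inside group 4.** Let s be the share of eligible fathers taking both surveys and d the share of those dropped for missing items. Share = s·d / [(1 − s) + s·d].

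- s = 0.70, d = 0.008 (co-parenting at m = 2%): 0.0056 / 0.3056 = 1.8%
- s = 0.70, d = 0.20: 0.14 / 0.44 = 31.8%
- s = 0.90, d = 0.15: 0.135 / 0.235 = 57.4%

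Neither end is a bound. The 10-item parenting composite at m = 2% with s = 0.70 gives 0.70 × 0.0017 = 0.0012, and 0.0012 / 0.3012 = 0.4%.

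**5. How pooling blurs a difference.** Suppose a characteristic is present in 30% of analysed and 60% of item-dropped fathers (assumed). Group 4 shows d × 0.60 + (1 − d) × 0.30: 33.0% at d = 0.10 and 36.0% at d = 0.20. The 30-point contrast between analysed and dropped fathers appears nowhere in the four-group table.

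**The case against.** **The wording can be read more kindly.** The sentence "We will conduct response rate analysis for each primary outcome of interest" comes before the four groups, and an outcome-specific response rate does not need them. The groups could also be meant to be built outcome by outcome, with a complete case being a father with usable values at both surveys. This stands in part: a reader might infer that a per-outcome check is impossible, and the documents do not support that. But the groups as written refer to surveys completed, and an analyst following them literally would describe the wrong group.

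**Ineligible is not non-respondent.** A reader might count everyone removed by a sample rule as hidden loss. That is wrong. A father with no child aged 24 or younger, or who already held the account, is outside that outcome's population. A rate over all consented fathers would repeat the error: if half already had a checking account and everyone answered every item, it would read 50% with no non-response.

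**The contact rule does not work the same way everywhere.** For the parenting behaviour composite, fathers who did not see the child are scored and kept. The rule clearly removes fathers only for the hours item. The sample column for the parenting composite shows the contact restriction, which conflicts with the scoring rule.

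**The gap may be small.** Protocol section 9.2 has the Data Manager proctor both surveys and help participants, which may limit blank items.

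**Some text cannot be seen.** There is an ellipsis just before this section of the SAP, and the Appendix B diagram is not in the text available. Any statement about what is absent is limited to the displayed text.

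**It is a supporting diagnostic in a descriptive study.** True, and no estimate or test changes. But it is the SAP's stated means of assessing non-response bias.

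**Conclusion.** The concern holds in a limited form. Among eligible fathers, those who took both surveys but have no usable change score are labelled complete cases although they are not in that outcome's t-test or, for the account outcomes, its reported percentage. This follows from the text and does not depend on any assumed rate.

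The size is unknown. Under assumed both-survey and item-loss rates, the share of loss inside group 4 runs from about 2% to 57%. A reader might infer from the upper figure that most loss is hidden; the documents do not support that, because with few blank items the share is negligible. Nor do they show that the missing answers are selective. It is a correction worth making before analysis, and it leaves the planned tests as they are.

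**What to change.** Amend Assessing non-response bias as follows, for each outcome:

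1. Define the eligible fathers first. Report those outside the outcome's population (no child aged 24 or younger where that applies, or account already held at entry) as ineligible.
2. Split group 4 into 4a, change score (or exit account status) observed, and 4b, both surveys taken but that value missing, with the reason (single item blank, or too many composite items blank).
3. Compare 4a with 4b and with groups 1 to 3 on the ACS variables already listed.
4. Report the response rate as 4a divided by eligible consented fathers. Where eligibility is known only from the entrance survey, state that the denominator is limited to fathers who took it.
5. For the hours item, show separately the fathers left out because they had not seen the child in the past month, since that rule depends on contact.
6. For the parenting composite, reconcile the matrix sample column with the rule that scores such fathers at the lowest value and keeps them.

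No new data are needed. The cost is a short SAP edit and a few extra table columns per outcome.

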1.2. OUTCOME RESEARCH QUESTIONS

For each outcome research question listed above, whether a descriptive or impact design, summarize the inputs (e.g., program components, program supports, implementation features, etc.), target population (e.g., the population for which the effect will be estimated) and the outcomes (e.g., child well-being, father-child engagement, etc.) that will be examined to answer the research question(s). Comparisons for descriptive evaluations may reflect circumstances before the grant, pre-treatment, or pre-determined benchmark from other studies with similar interventions.

Research Question Number Should correspond to the number indicated in Table 1.1 above	Intervention Program component or set of activities that the evaluation will test or examine	Target Population Population for which the effect of the treatment will be estimated	Comparison What the intervention will be compared to (e.g., pre-intervention for descriptive designs)	Outcome Changes that are expected to occur as a result of the intervention	Confirmatory or Exploratory? Confirmatory: those upon which conclusions will be drawn Exploratory: those that may provide additional suggestive evidence
R1	SFSF primary workshop curricula (40 hours)	Low-income, minority, young fathers (and father figures) in the Greater Memphis area	Pre- intervention	Improved co- parent relationships	Confirmatory
R2	SFSF primary workshop curricula (40 hours)	Low-income, minority, young fathers (and father figures) in the Greater Memphis area	Pre- intervention	Improved parenting relationships	Confirmatory
R3	SFSF primary workshop curricula	Low-income, minority, young fathers (and father figures) in the Greater Memphis area	Pre- intervention	Improved economic stability	Confirmatory

^{*} you may add rows by hitting the tab button, or right click and select insert row below

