5. RESEARCH DESIGN

For each research question, briefly describe why the research design proposed will answer each research question(s). State whether the proposed evaluation is a descriptive or impact evaluation and justify why the proposed research design is best suited to answer the research question(s).

Research Question	Design	Justification
I1	Assessment of fidelity to program model by tracking programmatic activities on nFORM.	Ensuring full program implementation to ensure that the intervention that is being measured is actually being delivered.
12	Assessment of dosage by measuring the number of primary workshop hours received and exploration of	Ensuring sufficient dosage is being delivered to adequate number of participants and exploring what characteristics are associated with greater workshop participation.

	variation by workshop and participant characteristics	
R1	Pre to post outcome assessment of program participation for improved co-parenting relationships	Significant improvement in co-parenting relationship outcomes from pre to post estimates the maximum amount of benefit that can be attributed to Seedco services in the absence of a counterfactual.
R2	Pre to post outcome assessment of program participation for improved parenting relationships.	Significant improvement in parenting relationship outcomes from pre to post estimates the maximum amount of benefit that can be attributed to Seedco services in the absence of a counterfactual.
R3	Pre to post outcome assessment of program participation for improved economic stability.	Significant improvement in economic stability outcomes from pre to post estimates the maximum amount of benefit that can be attributed to Seedco services in the absence of a counterfactual.

^{*} you may add rows by hitting the tab button, or right click and select insert row below

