9.2. METHODS OF DATA COLLECTION

If the evaluation will collect multiple waves of data, describe the timing of these waves below. When describing follow-up periods, specify whether the follow-up period will be post-baseline, post-random assignment, or post-program completion.

Wave of Data Collection	Timing of Data Collection
(e.g., baseline, short-term follow-up, long-term follow-up)	
Pre-Test (Wave 1)	Collected immediately following informed consent and study enrollment – during orientation session or first workshop

	Collected after the completion of core curriculum/primary workshop programing – during the last workshop session – approximately 8 weeks after enrollment/baseline
--	--

For each measure, describe how data will be collected detailing which data collection measures will be collected by which persons, and at what point in the programming or at what follow-up point.

Measure	Timing of Data Collection (baseline, wave of data collection)	Method of Data Collection	Who Is Responsible for Data Collection?	Impact Evaluations Only: Will Methods or Collection Procedures Differ by Study Group?	Administrative Data Only: Will data access require data sharing agreement?
nFORM Entrance Survey	Wave 1	Participant self-enters survey using online data collection platform	Data Manager will proctor data collection and assist participants as necessary		N/A
nFORM Exit Survey	Wave 2	Participant self-enters survey using online data collection platform	Data Manager will proctor data collection and assist participants as necessary		N/A

^{*} you may add rows by hitting the tab button, or right click and select insert row below

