Dosage will be measured by percent of target primary workshops participants attend on average (using 90% as a benchmark), and categories of attendance (initial, halfway, 90%, 100%) will be reported and compared to targets established by the program and reported on page 3 above. Exploratory analysis will examine how dosage varies by workshop characteristics (e.g., timing and length of sessions) and participant characteristics (e.g., age, employment status, relationship status)?

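### The paired t-tests treat fathers' change scores as independent, although the programme is delivered in workshops; if change correlates within workshop groups, five outcome tests overstate significance

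*SAP*

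**What the plan says.** The only significance test for outcomes is in the SAP, Analytic approach: "We will use paired sample t-tests to assess the magnitude and significance of changes among program participants in the analytic sample for each outcome". The measure tables (Protocol 9.1; SAP, Defining analysis measures) imply five tested outcomes: the co-parenting composite (R1); the parenting-behaviour composite, daily hours and contact frequency (R2); and difficulty paying bills (R3). The checking and savings account measures in R3 are reported as percentages without a test.

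On p-values the SAP adds: "We will adjust our p-values for multiple hypothesis testing and report the adjusted p-values in the appendix of the final report".

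Protocol 1.2 describes the intervention for R1 and R2 as "SFSF primary workshop curricula (40 hours" and for R3 as the same curricula without the hours. It labels all three questions confirmatory, defined as "Confirmatory: those upon which conclusions will be drawn". Protocol 5 says of R2, with parallel wording for R1 and R3: "Significant improvement in parenting relationship outcomes from pre to post estimates the maximum amount of benefit that can be attributed to Seedco services". Protocol 8.1 makes the father the unit of analysis. Protocol 9.2 places the exit survey "during the last workshop session".

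Workshop-level factors enter only the dosage analysis: "Exploratory analysis will examine how dosage varies by workshop characteristics (e.g., timing and length of sessions". The available text of the outcome analysis contains no workshop-group term, robust standard error, ICC or design effect. Appendix B, which the SAP cites for the anticipated sample size, is not part of that text.

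**The concern.** A paired t-test is a one-sample t-test on change scores, and its standard error is right only if those scores are independent across fathers. Fathers in one workshop group would share sessions and the occasion of the exit survey. Subtracting the pre-score removes stable differences between groups. It does not remove change that a group has in common, for instance because its sessions went well or badly.

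If such shared change exists, the standard error is too small, intervals are too narrow and significance is declared too often. There is no comparison arm, so the claim of improvement rests on this one standard error. A multiplicity adjustment corrects for the number of tests. Applied to p-values that are already too small, it leaves the dependence in place. Nothing planned would show whether the problem is present, because no ICC of change is to be reported.

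**Working it through.** The plan gives no significance level, power, detectable change or analysed sample size for these tests in the available text, so there is no design figure to reproduce.

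**Inputs**
- From the documents: 1,418 targeted graduates (Protocol 1, participation targets: 158 + 4 × 315). This stands in for the analysed N, as does half of it, 709. Both are illustrative.
- Assumed: two-sided 5% level; 8 to 20 analysed fathers per group (m); ICC of change 0.01 to 0.10. The 12 per group and ICC 0.05 case is a point inside the range, not a best estimate.

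**Formulas**
- Design effect: DE = 1 + (m − 1) × ICC. The true standard error is √DE times the paired one.
- Actual size of a nominal 5% test: 2 × [1 − Φ(1.96/√DE)]. Interval coverage is 1 minus that.
- Smallest observed change called significant, in SDs of the change score: paired 1.96/√N; clustered t(0.975; N/m − 1) × √(DE/N).

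**Test size**

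| m | ICC | DE | √DE | Actual size | Coverage of nominal 95% interval |
|---|---|---|---|---|---|
| any | 0 | 1 | 1 | 5% | 95% |
| 8 | 0.01 | 1.07 | 1.03 | 5.8% | 94.2% |
| 12 | 0.05 | 1.55 | 1.24 | 11.5% | 88.5% |
| 20 | 0.10 | 2.90 | 1.70 | 25.0% | 75.0% |

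**Smallest significant change, N = 1,418.** Paired: 1.96/√1,418 = 0.052. Clustered:
- m = 8, ICC 0.01 (about 177 groups): 1.974 × √(1.07/1,418) = 0.054
- m = 12, ICC 0.05 (about 118 groups): 1.980 × √(1.55/1,418) = 0.065
- m = 20, ICC 0.10 (about 71 groups): 1.994 × √(2.90/1,418) = 0.090

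**N = 709.** Paired: 1.96/√709 = 0.074. The clustered figure depends on how the sample was halved.

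| Case | Half as many groups, m unchanged | Same groups, m halved (4, 6, 10) |
|---|---|---|
| ICC 0.01 | 0.077 (size 5.8%) | 0.075 (DE 1.03, size 5.3%) |
| ICC 0.05 | 0.094 (size 11.5%) | 0.083 (DE 1.25, size 8.0%) |
| ICC 0.10 | 0.130 (size 25.0%) | 0.103 (DE 1.90, size 15.5%) |

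The right-hand column applies if fathers are lost through missing surveys or items spread across all groups.

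**Check of the remedy.** In 5,000 simulated trials per layout, with 10 to 118 equal groups of 12 or 20, the clustered test ran at 4.5% to 5.5%. The paired test ran at 4.6% to 5.4% at ICC 0 and at 11.0% to 24.9% at ICC 0.05 to 0.10. With unequal groups the clustered test ran at 4.9% to 6.4% for 20 or more groups and 5.7% to 7.1% for 10 to 12. With 20% of fathers assigned to a random group and ICC 0.05 to 0.10, it ran at 6.3% to 8.6%, against 11.0% to 26.0% for the paired test.

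**The case against.** The premise is partly inferred. The documents do not say that fathers move through in fixed groups, and they give no number of groups. The entrance survey may be taken at orientation or at the first workshop, so the pre-test occasion need not be shared by the group. Participants enter their own answers, and the outcomes concern each man's own child, co-parent and bills. Case management and employment support are also part of the service and are not described as group-delivered. An ICC of change near zero fits the text as well as 0.05 or 0.10 does. All of this stands, and it makes the point conditional.

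The consequence can also be small. A verdict changes only for an observed change between the paired and clustered thresholds, for example 0.052 to 0.065 SD at N = 1,418 with 12 per group and ICC 0.05. The study is called descriptive, and Protocol 5 already reads the result as an upper limit in the absence of a counterfactual. That narrows the stakes. It does not remove them, because the questions are labelled confirmatory and the reading depends on significance.

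A reader might infer that the tests will be wrong one time in four, that the estimated improvements are biased, or that every R3 result is affected. The documents support none of these. The 25% figure needs both upper-end assumptions at once. Clustering leaves the mean change as it is. Two of the three R3 measures have no test.

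**Conclusion.** The point holds in conditional form. The planned tests for the five non-binary outcomes make no allowance, in the available text, for change shared within workshop groups. Whether this inflates the error rate depends on an ICC that the plan neither gives nor would report. Under the assumed ranges the inflation runs from slight to serious (11.5% for a nominal 5% test at 12 analysed fathers per group and ICC 0.05), and it is nil at ICC 0. For a given group size at enrolment, loss of fathers spread across the groups makes it smaller. The change is worth making because its cost is low if the ICC is zero, while the paired test would give no warning if it is not.

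**What to change.** In the SAP, Analytic approach:

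1. Replace each paired t-test with an intercept-only regression of the change score, with standard errors clustered on workshop group and a t reference on (number of groups − 1) degrees of freedom. The point estimate is the same.
2. First confirm that the nFORM export identifies the workshop group; Protocol 11.2 lists only the client ID. The SAP's statement that "we assume that any primary or support services received by a participant are being accurately logged into nFORM" and its plan to analyse dosage by workshop characteristics make such a link plausible but do not establish it.
3. Fix in advance a rule that assigns each father to one group, for example the one where he attended most primary workshop hours. If attendance records cannot supply the group, use the session in which he took the exit survey, provided that can be identified.
4. Report the number of groups and the ICC of change for each outcome, and note as a limitation any outcome with fewer than about 20 groups.
5. Apply the planned multiplicity adjustment to the clustered p-values.

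**Cost.** SAP wording and one model option, with no new data collection if the group can be identified. At 12 per group, intervals are 1% to 2% wider at ICC 0 (118 and 59 groups: 1.980/1.960 and 2.002/1.960). At ICC 0.05 they are about 26% to 27% wider (0.0655/0.0520 and 0.0936/0.0736). Fathers who changed groups need the assignment rule, and wrong assignment leaves the correction incomplete.

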Economic Stability	Difficulty paying bills (categorical, scale from 1 to 4 where 1 is never and 4 is very often). Improvement will be measured by change score in participant's reported difficulty, calculated by subtracting their	nFORM Community-Based Fathers Survey B4, B3, B3a.	N/A (individual items will not be combined)

post-program value from their pre-program value.	
Has savings account at end of program, among those who came into the program with no savings account	
Has checking account at end of program, among those who came into the program with no checking account	

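### R3's checking- and savings-account measures count only accounts opened, so they cannot show whether account holding rose or fell, or whether a change is significant

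*SAP*

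**What the plan says.** - **The question.** Protocol 1.1 lists R3 as a primary outcome question asking about significant increases in economic stability. Protocol 1.2 marks the R3 row confirmatory, and Protocol 5 says a significant pre-to-post improvement is what will answer it.
- **The measures.** Protocol 9.1 gives three: difficulty paying bills, savings account and checking account. It notes that "individual items will not be combined".
- **Protocol definition of the account measures.** "Has savings account at end of program, among those who came into the program with no savings account" and "Has checking account at end of program, among those who came into the program with no checking account".
- **SAP definition (measure matrix).** "Binary measure of having opened a checking account by the end of the program" and "Binary measure of having opened a savings account by the end of the program", each scored 0/1, with both nFORM surveys listed as sources.
- **SAP analysis (Analytic approach).** "The main goal of this descriptive study is to assess pre-post change scores in the outcomes listed above among program participants". Paired t-tests are then planned for every outcome. The next sentence treats the binary measures separately: "For binary economic stability outcomes, we will descriptively report the percent of participants who opened a checking or savings account". Adjusted p-values will be reported; no adjustment method is named.
- **SAP missing-data rule for single items.** "participants who do not respond to the item on either the pre- or post-survey will be excluded from the analytic sample".

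**The concern.** A father can gain an account between the surveys or lose one. Both bear on whether economic stability improved, and the account measures record only the gain. The resulting figure cannot fall below zero. When nothing has truly changed, inconsistent answers at the two surveys can only push it above zero. Reported under a confirmatory question about significant increases, it could be taken as evidence of net improvement that it does not contain. Of R3's three measures, only difficulty paying bills can move both ways and has a clearly planned test. The supplied text does not say that R3's significance judgement rests on that item.

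**Working it through.** The documents give no rates for account holding, opening, loss or misreporting, and no sample size for these measures, so there is no planned figure to reproduce. **Every rate below is an assumption for illustration.**

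**1. What the measure can register.** In the Protocol 9.1 subset every father starts at 0, so change is 0 or +1. That is consistent with the SAP's change-score rule, but fathers who held an account at entry are outside the subset. The SAP denominator is less clear: the Sample cells for the account rows are not readable in the supplied text, and the Analytic approach speaks of participants without restriction. If all participants are the denominator, the 0/1 score is still for having opened an account, so losses remain uncounted.

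**2. One reported result, three net changes.** Assume n = 500 pairs, 250 holding at entry, and b = 25 of the 250 others opening an account; c holders lose theirs. The planned figure is 25/250 = 10% on the Protocol denominator, or 25/500 = 5% on all participants, whatever c is. The net change is d = (b - c)/n, with SE = sqrt(b + c - (b - c)²/n)/n.

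| c lost | Net change, points | 95% CI | Exact McNemar p |
|---|---|---|---|
| 5 | +4.0 | 1.9 to 6.1 | 0.0003 |
| 25 | 0.0 | -2.8 to 2.8 | 1.00 |
| 30 | -1.0 | -3.9 to 1.9 | 0.59 |

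For c = 5: SE = sqrt(30 - 400/500)/500 = 0.0108, and 4.0 ± 1.96 × 1.08 gives 1.9 to 6.1.

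**3. Loss rate that cancels the gain.** With holding p at entry and opening rate a among the rest, net change is zero when the loss rate among holders is a(1 - p)/p.

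| Holding at entry | 40% | 50% | 60% | 70% |
|---|---|---|---|---|
| a = 10% | 15% | 10% | 6.7% | 4.3% |
| a = 5% | 7.5% | 5.0% | 3.3% | 2.1% |

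**4. Misreporting with no true change.** Let each survey carry a symmetric error rate e, with error correlation r between surveys. Among fathers recorded as having no account at entry, the apparent opening rate is e(1 - e)(1 - r)/[pe + (1 - p)(1 - e)]. For e from 1% to 5% and p from 30% to 70%, this is 1.4% to 15% if r = 0 and 0.7% to 7.4% if r = 0.5. With all participants as denominator and r = 0 it is e(1 - e), about 1.0% to 4.8%.

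**5. Would a t-test on the Protocol subset help?** If k of n fathers, all 0 at entry, open an account, t = sqrt(k(n - 1)/(n - k)). At n = 250, k = 3 gives p = 0.083. At k = 4, t = sqrt(4 × 249/246) = 2.01 and p = 0.045. From n = 20 to n = 1,418 (the Protocol's target for 90% attendance, used as an upper case), four openings give p = 0.042 to 0.046. Such a test can only move upward, so it says nothing about net change.

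**The case against.** The strongest reply is that the SAP made an open choice. It calls the study descriptive, promises no p-value for accounts and makes no claim about net account holding. Helping fathers without an account to open one is a legitimate programme target, defined in the Protocol. The confirmatory label attaches to R3 as a question, not to each measure, and difficulty paying bills supplies a two-directional test. All of this stands. What it leaves is an unstated link: the reader must work out by elimination which measure carries R3's significance judgement.

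It can also be said that the planned paired t-tests cover all outcomes, including accounts. The sentence that follows sets the binary measures apart, so the better reading is that they have no test. This is an inference, and an ellipsis in the SAP suggests that some text may not be in the supplied copy. If the t-test did apply to the Protocol subset, step 5 shows that it would not answer the question.

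Finally, the zero and negative cases in step 2 need 10% and 12% of holders to lose an account in about 8 weeks (Protocol 9.2), and no document supports such rates. That is a fair limit on the size of the problem. Lower loss rates suffice when holding is common or uptake is small, and misreporting needs no true turnover.

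A reader might infer that R3 cannot be tested, or that the account figures will overstate benefit. The documents support neither: R3 keeps a tested measure, and no rate is available from which to estimate a bias.

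**Conclusion.** The point holds in a limited form. As written, the two account measures cannot show whether account holding rose or fell overall, and on the better reading of the SAP they carry no test or interval. That accounts lost go uncounted is true under either denominator. The restriction to fathers without an account rests on Protocol 9.1 alone, and the 10% and the 1.4% to 15% figures depend on it. The harm is a possible misreading of unknown size, not a demonstrated bias. It is worth correcting because the remedy is cheap and the question is labelled confirmatory.

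**What to change.** For each account type, among fathers who answered the item at both surveys:

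- report percent holding at entry, percent holding at exit, and the paired difference with a 95% CI;
- report percent opened among those without an account beside percent lost among those with one;
- state each denominator.

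If any R3 conclusion will be drawn on accounts, base it on the paired difference, test it with McNemar's test and include both tests in the multiplicity adjustment. If not, add one sentence: the two account measures are exploratory, and R3's significance judgement rests on difficulty paying bills.

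**Cost.** Two extra 2x2 tables and SAP wording. Both surveys are already listed as sources, so no new data are expected. The instrument is not shown, so any skip pattern between items B3 and B3a must be checked. The account figure may look less favourable. If the two tests are added, the family grows from 5 (co-parenting, parenting behaviours, hours, contact frequency, bills) to 7. Under Bonferroni (assumed) the per-test level falls from 0.0100 to 0.0071, and the detectable effect at 80% power rises by (2.690 + 0.842)/(2.576 + 0.842) = 1.033, about 3.3%. The exploratory option adds no tests to the family.
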